#### **9.2.7. Dosing and Treatment Exposure**

Descriptive statistics for the duration of treatment will be summarized by treatment group for Part A and Part B for the Safety, m-MITT, and CRABC m-MITT Populations. Duration of treatment will be calculated as the last dose date - the first dose date + 1 day. Contingency table will be provided to show the number and percentage of patients in each treatment group with duration of treatment in the following categories: 1-3 days, 4-7 days, 8-10 days, and > 10 days. The total number of doses of study drug received will also be summarized by treatment group using descriptive statistics.

The compliance rate of study drug will be calculated as the total number of doses received divided by the total number of doses expected then multiplied by 100. The total number of expected doses is the number of medication days multiplied by the number of expected doses per day. Number of medication days is the total number of days from the date of the first dose of study drug to the date of the last dose of study drug.

Percent compliance to study drug will be calculated using the following formula:

$$\% \text{compliance} = \frac{\text{no. of doses received} * 100}{\text{total no. of doses expected}}$$

Percent compliance will be summarized by treatment group for the Safety, m-MITT, and CRABC m-MITT Populations. In addition, contingency tables will be provided to show the number and percentage of patients in each treatment group with compliance in the following categories: <80% and ≥80%.

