### 5.3 Dosing in Patients With Renal Insufficiency

Estimated creatinine clearance will be determined daily while patients are receiving IV study drug. Principal Investigators will be responsible for testing estimated creatinine clearance daily at the local laboratory per institutional Standard Operating Procedures and must adjust doses of all medications as detailed in Table 1 in order to optimize efficacy and safety. Estimated creatinine clearance and dose adjustment data will be captured in source documents and in the eCRFs. Table 1 summarizes the recommended dosing regimens for patients with renal impairment. Of note, patients with estimated creatinine clearance <15 mL/min will only be dosed with imipenem/cilastatin as outlined in Table 1 if renal replacement therapy of acute hemodialysis is planned to be instituted within 48 hours of dosing.

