**Table 1. Study Drug Dose Adjustments by Renal Function**

Estimated Creatinine Clearance, mL/min (Cockcroft-Gault)	ETX2514SUL Dosage Regimen	Colistin Dosage Regimen	Imipenem/Cilastatin Dosage Regimen [1]
130-200 (augmented renal clearance)	1.5/1.5 g q6h	2.5 mg/kg q12h	1.0/1.0 g q6h
90-129 (normal)	1.0/1.0 g q6h	2.5 mg/kg q12h	1.0/1.0 g q6h
60-89 (mild renal impairment)	1.0/1.0 g q6h	1.25 to 1.9 mg/kg q12h	0.75/0.75 g q8h
30-59 (moderate renal impairment)	1.0/1.0 g q6h	1.25 mg/kg q12h or 2.5 mg/kg once daily	0.5/0.5 g q6h
15-29 (severe renal impairment)	1.0/1.0 g q8h	1.5 mg/kg q36h	0.5/0.5 g q12h
0-14 (severe renal impairment) [2]	1.0/1.0 g q12h	1.5 mg/kg q36h	0.5/0.5 g q12h
Intermittent hemodialysis	1.0/1.0 g q12h [4]	Non-dialysis day: CBA dose of 65 mg q12h. Dialysis day supplement: add 40 mg (for 3-hour IHD session) or 50 mg (for 4-hour IHD session) post-dialysis [3]	0.5/0.5 g q12h [4]
Continuous renal replacement therapy	1.5/1.5 g q6h	220 mg q12h	1.0/1.0 g q8h to q12h, depending on ultrafiltration rate

 
Administer doses ≤0.5 g by IV infusion over 20 to 30 minutes. Administer doses >0.5 g by IV infusion over 40 to 60 minutes. In patients who develop nausea during the infusion, the rate of infusion may be slowed.
 
Patients with creatinine clearance <15 mL/min should not receive imipenem/cilastatin unless renal replacement therapy of acute hemodialysis is instituted within 48 hours of dosing.
 
The dialysis session should occur toward the end of a colistimethate dosing interval, and the supplement to the baseline (non-dialysis) daily dose should be administered with the next regular dose, after the dialysis session has ended.
 
The dialysis session should occur toward the end of a dosing interval, and the daily dose should be administered after the dialysis session has ended.
 
 
CBA = colistin base activity; ETX2514SUL = sulbactam-ETX2514; IHD = intermittent hemodialysis; IV = intravenous; q6h = every 6 hours; q8h = every 8 hours; q12h = every 12 hours; q36h = every 36 hours.
			

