### 5.5.3 Study Drug Administration

The pharmacist (or qualified designee) will be responsible for providing study personnel with study drug ready for IV infusion. Patients will receive treatment in accordance with the randomization schedule provided via the IRT system. Patients will receive randomized treatment administered as described in the Pharmacy Manual.

Patients will receive all infusions by programmable infusion pump, or drip infusion in case of failure of the pump, while seated or partially reclined in bed. The times at which each infusion is started and stopped must be recorded. If a dose is interrupted for more than 10 minutes, the interruption and reason for interruption should be noted in the source documents. Any missed dose should also be noted in the source documents with the reason for the missed dose. For patients with normal renal function, study drug infusions will be administered q6h ( $\pm 15$  minutes) for ETX2514SUL and imipenem/cilastatin and q12h ( $\pm 15$  minutes) for colistin. Infusions that fall outside of the q6h ( $\pm 15$  minutes) or q12h ( $\pm 15$  minutes) dosing schedule will be considered protocol deviations. It is critical that administration and infusion time be captured in the eCRF based on actual time. Windows for administration and infusion should be used sparingly, and the patient should remain on schedule based on the q6h administration requirement.

Dosing time is relative to the start of infusion. For additional information on study drug product dilution, infusion volumes, and dispensing instructions, refer to the Pharmacy Manual.

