with evidence of carbapenem resistance should remain on their assigned treatment regimen; treatment regimen changes can occur after 5 days after discussion with the Medical Monitor. If changes to the regimen are needed due to unsatisfactory clinical response, patients should be classified as clinical failures and discontinued from study drug. All patients should receive at least 48 hours of IV study drug (ie, 8 doses of ETX2514SUL plus 8 doses of imipenem/cilastatin or 4 doses of colistin plus 8 doses of imipenem/cilastatin in patients without dose adjustments) before the Investigator considers the patient to be a clinical failure and discontinues the patient from study drug therapy.

Note: Patients who experience focal tremors, myoclonus, or seizures at any point during the study should be evaluated neurologically, placed on anticonvulsant therapy (if not already instituted), and the dose of imipenem/cilastatin should be evaluated to determine whether it should be decreased or discontinued.

Day 1 is defined as the first day of study drug administration. The subsequent study days are defined by the number of treatment days thereafter. Treatment days should constitute 24 hours of treatment. For those patients with no dose adjustments, the duration of antibiotic treatment with study drug therapy will be 28 doses of ETX2514SUL plus 28 doses of imipenem/cilastatin or 14 doses of colistin plus 28 doses of imipenem/cilastatin (ie, treatment for 7 days for those without dose adjustments), with a prolongation of therapy up to 14 days if clinically indicated. Refer to the Pharmacy Manual for specifics on dosing for all patients.

The overall study design is shown in the figure below.

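### SAP 9.2.7 counts expected doses by whole calendar dates; on the inclusive count, fully dosed short courses can be tabulated as under 80% compliant because of the hour they started

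*SAP*

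**What the plan says.** Protocol 5.5.4 leaves the compliance calculation to the SAP. SAP 9.2.7 defines the denominator in two sentences: "The total number of expected doses is the number of medication days multiplied by the number of expected doses per day", and "Number of medication days is the total number of days from the date of the first dose of study drug to the date" (the end point being the final dose). The same section says "Duration of treatment will be calculated as the last dose date - the first dose date + 1 day", but it does not repeat the added day for medication days. It does not prorate a first or last date on which only some doses could have been given.

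On use of the result, the SAP says "Percent compliance will be summarized by treatment group for the Safety, m-MITT, and CRABC m-MITT Populations", with patients also split at 80%.

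Elsewhere the SAP works in elapsed time. SAP 3.1 treats a day of therapy as a 24-hour block and requires "at least 48 hours of IV study drug (ie, 8 doses of ETX2514SUL plus 8 doses of imipenem/cilastatin", or 4 colistin doses with the same imipenem/cilastatin, before failure is declared. SAP 8.5 equates 72 hours with 12 six-hourly or 6 twelve-hourly doses. The full 7-day course is 28 or 14 doses.

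**The concern.** A patient whose first dose is in the afternoon cannot receive a full day's doses on that date, and usually not on the last date either. A denominator that charges a full day's doses to both dates is too large. The excess is at most about one day's doses, so it matters most for short courses. The plan expects such courses: SAP 9.2.7 has its own 1-to-3-day duration category, failure can be declared after 48 hours, and patients with a positive rapid test but no culture growth stop study drug yet stay in the Safety Population (SAP 8.2).

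At stake is whether the 80% split in the exposure tables reflects missed doses or the clock time of the first dose.

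**Working it through.** **Inputs.** Six-hourly dosing is 4 doses a day and twelve-hourly is 2 (regimens in SAP 3.1). Course lengths are from SAP 3.1 and 8.5. The cut is 80% (SAP 9.2.7).

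**The plan's own dose counts.** Hours divided by interval: 48/6 = 8, 72/6 = 12, 168/6 = 28; 48/12 = 4, 72/12 = 6, 168/12 = 14. All match the documents.

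**Formula.** For N on-time doses with the first at clock hour h:
- last start = h + interval × (N − 1)
- dates touched, D = floor(last start / 24) + 1
- inclusive score = N / (D × doses per day)
- plain-difference score = N / ((D − 1) × doses per day)

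**Inclusive count, no dose missed.** *Early* means before 06:00 for six-hourly and before noon for twelve-hourly dosing.

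| Course | Last start | Early start | Later start |
|---|---|---|---|
| 8 six-hourly | h + 42 | D = 2, 8/8 = 100% | D = 3, 8/12 = 66.7% |
| 12 six-hourly | h + 66 | D = 3, 12/12 = 100% | D = 4, 12/16 = 75.0% |
| 28 six-hourly | h + 162 | D = 7, 28/28 = 100% | D = 8, 28/32 = 87.5% |
| 4 twelve-hourly | h + 36 | D = 2, 4/4 = 100% | D = 3, 4/6 = 66.7% |
| 6 twelve-hourly | h + 60 | D = 3, 6/6 = 100% | D = 4, 6/8 = 75.0% |
| 14 twelve-hourly | h + 156 | D = 7, 14/14 = 100% | D = 8, 14/16 = 87.5% |

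The longest perfectly dosed courses that can fall under 80% are 22 six-hourly doses (22/28 = 78.6%, start at or after 18:00), 14 eight-hourly doses (14/18 = 77.8%, start at or after 16:00) and 6 twelve-hourly doses.

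**Missed doses in a 7-day course.** With 25 of 28 six-hourly doses given, first and last included, true compliance is 25/28 = 89.3%. Started at or after 06:00, the course touches 8 dates and scores 25/32 = 78.1%.

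**Plain date difference.** Eight six-hourly doses score 8/4 = 200% (early start) or 8/8 = 100% (later). If all treatment falls on one date, D − 1 = 0 and no score exists.

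**24-hour treatment days (SAP 3.1).** Eight doses make 2 days and 8 expected doses, so 100% at any start hour. A ninth dose opens a third block; if that counts as a whole day the score is 9/12 = 75%. This reading cures whole-day courses only.

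**Replacement rule.** Expected = (last start − first start)/interval + 1 gives 42/6 + 1 = 8, 66/6 + 1 = 12, 162/6 + 1 = 28, 36/12 + 1 = 4 and 60/12 + 1 = 6: 100% for every on-time course, and 25/28 = 89.3% for the course with three missed doses.

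**Interval change.** Take six-hourly times at 0–42 h (8 times), then eight-hourly at 48–96 h (7 times), with the 36 h and 42 h doses missed. Counting scheduled times gives 13/15 = 86.7%. Applying the constant-interval formula to each period separately gives (30/6 + 1) + (48/8 + 1) = 6 + 7 = 13 expected and a false 100%, so scheduled times must be counted across the change.

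**The case against.** The strongest reply is that SAP 3.1 already defines treatment days as 24-hour blocks; read into 9.2.7, that makes the 48-hour, 72-hour and 7-day courses score correctly. This stands as a possible reading, but 9.2.7 gives its own definition in dates, which is what a programmer would follow. At the least, the two sections need reconciling.

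It is also fair that the under-80% misclassification depends mainly on the inclusive count. On a plain difference no fully dosed six-hourly course of 7 or more doses falls below 80%; the fault there is of another kind. And the planned minimum course is 28 or 14 doses, which does not cross the cut when fully dosed.

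Three stronger inferences are tempting and are not supported:
- *Patients would be lost from CE, ME and CRABC ME.* SAP 8.5 requires at least 80% of anticipated doses, but it neither defines that term nor refers to 9.2.7, and the same sentence sets its own 48-hour and 72-hour counts. No such effect is written.
- *The tables would show a false difference between arms.* The vulnerable start hours do differ (06:00 against noon), but both arms also receive six-hourly imipenem/cilastatin, and the SAP does not say how the two drugs of a regimen are combined.
- *The formula fixes one daily dose number whatever happens to renal function.* Under Protocol 5.3, investigators "must adjust doses of all medications as detailed in Table 1 in order to optimize efficacy and safety", and 9.2.7 does not say how a changed interval enters the count. That is missing detail; the text does not rule out a day-by-day figure.

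**Conclusion.** The rule as written gives wrong compliance values, at low severity. On the inclusive reading, perfectly dosed 48-hour and 72-hour courses can appear as 66.7% and 75.0% compliant solely because of start hour, and a 7-day course at 89.3% can appear as 78.1%. On the plain-difference reading, values exceed 100% or are undefined. The added day in the duration formula favours the inclusive reading but does not settle it.

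The effect is confined to the descriptive compliance summaries and the 80% split in the Safety, m-MITT and CRABC m-MITT Populations. The 28-day mortality analysis does not use compliance.

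The figures assume on-time dosing at a constant interval. How many patients would be affected cannot be stated, because the documents give neither the number of short courses nor the spread of start times. If start times were uniform over the day (an assumption), 18/24 = 75% of perfect 8- or 12-dose six-hourly courses and 12/24 = 50% of perfect 4- or 6-dose twelve-hourly courses would be tabulated below 80%.

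**What to change.** In SAP 9.2.7, replace the date-based denominator and reconcile it with SAP 3.1. For each drug, define expected doses as the number of scheduled dose times from the first dose start to the last dose start, using the interval prescribed at each time. For a constant interval this is (last start − first start)/interval + 1, rounded to the nearest whole number because Protocol 5.5.3 allows starts 15 minutes either side of schedule. Count through an interval change, so that doses missed next to it stay in the denominator. State that, as under the current rule, doses due after the last dose given are not counted.

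The cost is SAP wording and programming. Protocol 5.5.3 says "It is critical that administration and infusion time be captured in the eCRF based on actual time", and Protocol 5.3 puts dose-adjustment data there too. One check is needed first: Protocol 5.3 does not say that the time of each interval change is recorded. Dialysis-timed regimens, and the colistin row of Protocol Table 1 that allows either twelve-hourly or once-daily dosing, need a stated convention for scheduled times.

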### **9.3. Efficacy Analyses**

The efficacy analyses will be analyzed for Part A and Part B separately. Patients who were randomized into Part A and stayed in Part A will be summarized/analyzed only for Part A. Patients who were randomized into Part A but then transferred into Part B will be summarized/analyzed only for Part B.

#### **9.3.1. Primary Efficacy Analyses**

The primary efficacy endpoint for the study is 28-day all-cause mortality in the CRABC m-MITT Population in Part A. Patients in the CRABC m-MITT Population who discontinue study drug prematurely in Part A for any reason will be included in the assessment of 28-day mortality, provided consent has not been withdrawn. Patients who withdraw consent from the survival status will be excluded from the analysis. Patients who have missing survival status will be treated as death. Patients who were randomized into Part A but then transferred into Part B will not be included in Part A analysis.

The non-inferiority assessment will be based on the 2-sided 95% confidence intervals (CIs) computed using a continuity-corrected Z-statistic for the difference ( $[\text{ETX2514SUL} + \text{imipenem/cilastatin}] - [\text{colistin} + \text{imipenem/cilastatin}]$ ) in 28-day all-cause mortality rates between the treatment groups. Non-inferiority will be concluded if the upper limit of the 2-sided 95% CI is less than +20%. If non-inferiority is achieved, the superiority will be investigated. Superiority will be concluded if the upper limit of the 2-sided 95% CI is less than 0.

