### 6.3 Treatment Period – Day 1 Through End of Treatment

All patients will receive IV treatment for a minimum of 28 doses of ETX2514SUL plus 28 doses of imipenem/cilastatin or 14 doses of colistin plus 28 doses of imipenem/cilastatin (ie, 7 days of antibiotics for those without dose adjustments). Patients can receive up to 14 days of IV treatment if clinically indicated. Time of discontinuation of antibiotics will be determined on achievement of clinical cure (see [Section 7.6](#)). Additionally, at any time during the study, if a patient develops signs and symptoms of disease worsening, cultures from all appropriate sites should be collected and sent to the central laboratory.

#### 6.3.1 Day 1

The following procedures will be performed at Day 1:

- Record concomitant medications;
- Obtain vital signs, including blood pressure, heart rate, and respiratory rate, and, for ventilated patients, oxygen therapy and respiratory settings including FiO2 and PEEP;
- Assess clinical signs and symptoms (see [Section 7.5](#));
- Collect predose blood samples for:
  - Serum chemistry;
  - Serum creatinine;
  - Hematology; and
  - Blood cultures in patients with bacteremia, if applicable;
- Collect predose urine sample for urinalysis;
- Calculate APACHE II, SOFA, or qSOFA score prior to randomization;

Note: An APACHE II or SOFA score will be calculated prior to randomization for patients in Part A only. For patients who are not being treated in an intensive care unit and cannot have an APACHE II or SOFA score performed, and for all patients in Part B, a qSOFA score should be calculated.

- Randomize patient to study drug via IRT;
- Administer study drug;
- For intense PK sampling, collect PK samples after the second infusion at the end of the infusion after the infusion pump is turned off (+15 minutes), 1.5 hours ( $\pm$ 15 minutes) after the end of the infusion, and immediately prior to the start of the next infusion;

- For sparse PK sampling, collect PK samples after the second infusion, immediately prior to the start of the next infusion. The patient should have received at least 2 infusions before this schedule is implemented;

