### **3.3. Randomization and Blinding**

Qualifying patients enrolling in Part A will be randomized in a 1:1 ratio to receive 1.0 g ETX2514/1.0 g sulbactam q6h plus 1.0 g imipenem/1.0 g cilastatin q6h or 2.5 mg/kg colistin q12h plus 1.0 g imipenem/1.0 g cilastatin q6h via the Interactive Response Technology (IRT) system. Patients enrolled in the study based on the positive BPP rapid test results but are found to not grow ABC in respiratory specimen cultures by the local microbiology laboratory will be withdrawn from the study drug treatment as detailed in Protocol Section 4.3.

Randomization in Part A will be stratified by indication (HABP/VABP/VP versus bacteremia), severity of illness (based on APACHE II [10 to 19 versus 20 to 30], SOFA [7 to 9 versus  $\geq 10$ ], or qSOFA [2 versus 3] score at Screening), and geography (China Mainland versus Rest of World). In the situation where a patient has more than one score reported, the scores will be used in the following order: APACHE, SOFA, and qSOFA. A quick reference guide will be provided that describes the IRT system and includes user instructions.

The study data will be collected and handled as if it were a blinded study. The blinded assessor (see Section 3.3.2), the Sponsor, and the Sponsor's designees involved in medical and safety monitoring, data management, and other aspects of the study (eg, interpretation of the results) will be blinded to treatment assignment. Given the complexity of the regimens, the Principal Investigator, other care givers, the clinical research associate (CRA), and other site personnel (eg, study coordinators and pharmacy staff) will be unblinded (see Section 3.3.1). Patients will not be informed of their treatment assignment, and efforts will be made to keep patients naïve to their treatment throughout the course of the study.

Part B is open-label and not randomized; all patients enrolling in Part B will receive 1.0 g ETX2514/1.0 g sulbactam q6h plus 1.0 g imipenem/1.0 g cilastatin q6h.

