#### **9.1.3. Baseline Definition**

For microbiological data, baseline pathogen(s) are determined from the specimens collected prior to the first dose of study drug.

For all efficacy and safety endpoints, baseline is defined as the last measurement or assessment prior to the first dose of study drug.

For safety endpoints, patients who were randomized into Part A then transferred into Part B will be included in both Part A and Part B, baseline is defined as the last measurement or assessment prior to the first dose of study drug of Part A for both Part A and Part B safety analysis.

For efficacy endpoints, patients who were randomized into Part A then transferred into Part B will be included in Part B only, baseline is defined as the last measurement or assessment prior to the first dose of study drug of Part A for Part B efficacy analysis.

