### 9.2.3. Demographic and Baseline Characteristics

Demographics and baseline characteristics including age (as a continuous variable and categorized as <65, 65-75 and >75 years), sex, race, ethnicity, weight, body mass index (BMI) (as a continuous variable and categorized as <25, 25-<30, 30-<35 and  $\geq$ 35), creatinine clearance (as a continuous variable and categorized as <15 mL/min, 15-<30 mL/min, 30-<60 mL/min, 60-<90 mL/min and  $\geq$ 90 mL/min), Charlson Comorbidity Index <3 or  $\geq$ 3, septic shock status at baseline, mechanical ventilation status at baseline, infection type (bacteremia, HABP, VABP, VP, cUTI, AP, surgical wound infection, and post-traumatic wound infection), APACHE II score [<10, 10 to 19, 20 to 30 and >30], SOFA score [<7, 7 to 9 and  $\geq$ 10], qSOFA score [<2, 2, 3 and >3], severity of illness (APACHE II [10-19]/SOFA [7-9]/qSOFA [2] and APACHE II [20-30]/SOFA [ $\geq$ 10]/qSOFA [3]) will be summarized by treatment group and baseline infection type (Overall, Bacteremia, HABP, VABP, VP, cUTI, AP, Surgical Wound Infection, and Post-traumatic Wound Infection) in the ITT, m-MITT, and CRABC m-MITT Populations. The demographics and baseline characteristics will be summarized for all regions and repeated for Mainland Chinese patients.

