#### **Sensitivity Analyses**

Sensitivity analyses of the primary efficacy endpoint will be conducted as follows:

- Analysis of the primary efficacy endpoint will be performed for patients whose eligible culture is >48 hours prior to the first dose of treatment in the CRABC m-MITT Population.
- Analysis of the primary efficacy endpoint will be performed for patients whose eligible culture is ≤48 hours prior to the first dose of treatment in the CRABC m-MITT Population.
- Analysis of the primary efficacy endpoint will be performed for patients with ABC pathogens susceptible to ETX2514SUL and colistin at baseline in the CRABC m-MITT Population.
- Analysis of the primary efficacy endpoint will be performed for patients without ABC susceptibility results for ETX2514SUL or colistin at baseline in the CRABC m-MITT Population.
- Analysis of the primary efficacy endpoint will be performed including the patients who were randomized into Part A but then transferred into Part B in the ITT Population.
- Analysis of the primary efficacy endpoint will be performed excluding the patients who have missing survival status in the CRABC m-MITT Population.

Analysis of the primary efficacy endpoint and the sensitivity analysis will be repeated including the patients who withdraw consent from the survival status.

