### 9.3.2. Secondary Efficacy Analyses

The secondary efficacy endpoints for Part A and Part B include the following:

- 28-day all-cause mortality in the ITT Population;
- Clinical cure at TOC in the CRABC m-MITT Population;
- Clinical cure at TOC in the m-MITT, Clinical Evaluable (CE), Microbiologic Evaluable (ME), and CRABC ME Populations;
- Clinical cure at EOT, and LFU in the m-MITT, CRABC m-MITT, CE, ME, and CRABC ME Populations;
- Microbiological favorable assessment at EOT, TOC, and LFU by overall, monomicrobial infection and polymicrobial infection in the m-MITT, CRABC m-MITT, ME, and CRABC ME Populations. Monomicrobial infection is defined as subjects with only ABC pathogens isolated at Baseline, Polymicrobial infection is defined as subjects with both ABC pathogens and non-ABC pathogens isolated at Baseline;
- 14-day all-cause mortality in the CRABC m-MITT and m-MITT Populations; and
- 28-day all-cause mortality in the m-MITT and CRABC ME Populations.

All secondary efficacy analyses will be analyzed including the patients who withdraw consent from the survival status.

In addition, the primary analysis will be repeated for 28-day all-cause mortality in the ITT, m-MITT and CRABC ME Populations excluding the patients who withdraw consent from the survival status for Part A. 14-day all-cause mortality in the CRABC m-MITT and m-MITT Populations will be performed in a same manner excluding the patients who withdraw consent prior to Day 14 for Part A.

Similarly, the analysis of clinical response and the microbiologic response will be repeated excluding patients who withdraw consent from the survival status in the CRABC m-MITT Population for Part A.

The number and percentage of patients in each response category for the secondary efficacy endpoints will be summarized by treatment group. Two-sided 95% CIs computed using a continuity-corrected Z-statistic for the difference in outcome rates between the treatment groups in Part A will be provided. Patients who initially randomized to Part A and transferred to Part B will not be included in Part A analysis and will be included in Part B analysis from the time point of transfer. Patients with a missing secondary efficacy value, the efficacy variable will be considered as non-responder. In addition, time to death will be analyzed using log rank test between the treatment groups for Part A.

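### Part A is randomized by severity of illness, but no planned efficacy comparison is stratified by it; a severity-stratified estimate is a cheap robustness gain if severity predicts death, and its absence is not an error

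*SAP*

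**What the plan says.** SAP 3.3 (and Protocol 5.4): "Randomization in Part A will be stratified by indication (HABP/VABP/VP versus bacteremia), severity of illness", with geography as the third factor. Severity is a two-level variable built from whichever score is available at Screening; where there are several, "the scores will be used in the following order: APACHE, SOFA, and qSOFA".

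SAP 9.3.1, primary analysis: "The non-inferiority assessment will be based on the 2-sided 95% confidence intervals (CIs) computed using a continuity-corrected Z-statistic". Non-inferiority needs an upper limit below +20%, superiority an upper limit below 0. No stratum, weight or covariate is mentioned, and Protocol 9.2.2.1 mentions none.

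Under "Sensitivity analyses of the primary efficacy endpoint will be conducted as follows", the SAP lists analyses that change the patient set or the handling of missing survival status and withdrawn consent. None changes the estimator.

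SAP 9.3.2 adds that "time to death will be analyzed using log rank test between the treatment groups for Part A", again with no strata.

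Severity is otherwise tabulated by arm at baseline, including in the CRABC m-MITT Population (SAP 9.2.3), and used as a subgroup in a forest plot (SAP 9.3.4).

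**The concern.** The design treats severity as important enough to balance, yet the analysis does not use it. Two things could follow if severity predicts death.

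First, some precision is left unused: variation in mortality between severity levels stays in the crude standard error.

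Second, the balance bought at randomization is only partly kept. The primary population is about 60% of those randomized (SAP 4) and is fixed by later microbiology (SAP 8.4). A severity imbalance in it would be visible in the baseline tables, but the SAP has no prespecified estimate that accounts for it. The subgroup plot shows rates by severity and does not give an adjusted overall difference. An adjusted analysis added after the imbalance had been seen would be post hoc.

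**Working it through.** **1. The plan's own figure.** Inputs from SAP 4: mortality 41% and 36%, margin 20 points, 60 per arm.

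- SE = sqrt[(0.41×0.59 + 0.36×0.64)/60] = sqrt(0.4723/60) = 0.0887.
- Power = Φ(0.25/0.0887 − 1.96) = 80.5%. The stated 80% reproduces.
- With the SAP's continuity correction of 1/60: Φ(0.2333/0.0887 − 1.96) = 74.9%. This drop comes from the correction, which is a separate question, and not from the missing strata.

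**2. Assumptions.** The documents give neither the severity mix nor mortality by severity. Assumed: 200 randomized in permuted blocks of 4 within the eight strata (bacteremia 10%, China 20%, neither prognostic); 60% retained at random; half the patients in the severe level; a mortality gap D between levels, equal in both arms. D = 40 means 21% against 61% in the control arm, the extreme of the range.

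**3. Balance in the primary population.** The SD of the between-arm difference in percent severe would be sqrt(2×0.25/60) = 9.1 points under simple randomization. Stratified randomization followed by 60% retention reduces it to about 9.1×sqrt(1 − 0.6) = 5.8 points; simulation with incomplete blocks gives 6.0. So:

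- ETX2514SUL arm at least 5 points sicker: 1 − Φ(5/6.0) = 20% of trials, and as often at least 5 points healthier.
- At least 10 points sicker: about 4.7%, and as often at least 10 points healthier.
- Shift in the crude difference = imbalance × D. Its SD is 6.0 × 0.20, 0.30 or 0.40 = 1.2, 1.8 or 2.4 points, against a 95% half-width of 17.3 points.

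**4. Precision, by formula.** Stratifying removes q(1−q)D² per arm, with q = 0.5: v = 0.4723 − 0.5D². Corrected power is then 76.7%, 79.0% and 82.3% at D = 20, 30 and 40.

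**5. Simulation.** Crude interval against a Mantel-Haenszel difference with Sato variance by severity, both with the same term 0.5(1/n1 + 1/n2):

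| Gap D (points) | Crude power | Stratified power | Gain | Conclusions differ |
|---|---|---|---|---|
| 0 | 74.8% | 74.7% | −0.1 | – |
| 20 | 75.0% | 76.4% | +1.4 | about 4% |
| 30 | 75.5% | 78.9% | +3.4 | about 6% |
| 40 | 75.9% | 82.1% | +6.2 | about 8% |

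- One-sided error at a true +20 points: crude about 1.6% at D = 0, falling to about 1.2% at D = 40; stratified about 1.6% throughout.
- With a simple within-stratum variance instead of Sato, the cost at D = 0 is 0.7 points (75.0% against 74.3%).
- Without the continuity correction the gains are similar: −0.1, +1.2, +3.0 and +5.4.
- With 30% or 70% severe: about −0.1, +1.2, +2.8 and +5.1.
- If the recorded level disagrees with the severity that drives mortality in 20% of patients: −0.2, +0.4, +1.1 and +2.0.

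**6. Given an imbalance.** When the ETX2514SUL arm is at least 5 points sicker, crude power is 68.6%, 65.6% and 62.2% at D = 20, 30 and 40, against 76.2%, 78.5% and 81.7% stratified. When it is at least 10 points healthier, crude error is 2.6%, 3.7% and 4.2%, against 1.4–1.5% stratified.

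**7. Log-rank.** With 41% against an assumed 20% mortality, power at gaps 20, 30 and 36 is 72.0%, 72.3% and 72.7% unstratified and 72.5%, 73.5% and 74.6% stratified: a gain of under 2 points.

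**The case against.** The strongest reply is that this is a preference. The documents promise no stratified analysis, and Protocol Table 7 also uses a plain normal-approximation interval, so design and analysis agree. The crude error rate is below 2.5%. The benefit rests on a gap the documents do not give, is 1.4 points at D = 20, and shrinks further if the three-score composite measures severity imperfectly. All of this stands. It limits the weight of the point and leaves the omission in place.

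The conditional figures can also mislead. A reader might infer that about one trial in five reaches a wrong conclusion because of imbalance. That is not so: one in five is how often the ETX2514SUL arm is at least 5 points sicker, while the two methods disagree in only about 4% to 8% of trials.

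A reader might infer that the severity subgroup in SAP 9.3.4 is a different variable from the randomization stratum. The documents do not settle this. The stratum uses the Screening score, Protocol 6.3.1 lists for Day 1 "Calculate APACHE II, SOFA, or qSOFA score prior to randomization", and SAP 9.1.3 says "For all efficacy and safety endpoints, baseline is defined as the last measurement or assessment prior to the first dose of study drug". But that sentence concerns endpoints, and SAP 9.3.4 uses the same bands and refers only to baseline characteristics. The two values may differ; that they do is not shown.

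Finally, any recommendation must say whether the continuity correction is kept, because that choice moves power by about 80.5 − 74.9 = 5.6 points, more than stratifying does at gaps of 30 or less.

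**Conclusion.** The point holds as an improvement. That the analyses are unstratified is read from silence, but no section of either document points the other way.

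A reader might conclude that ignoring a randomization stratum invalidates the interval or undermines the 80% power. The documents do not support that: the crude interval is valid, becomes slightly conservative as severity becomes more prognostic, and the stated power reproduces without any stratification.

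What stratifying offers is about 1.4, 3.4 and 6.2 points of power at assumed gaps of 20, 30 and 40 points, for a cost of about 0.1 to 0.7 points if severity is not prognostic. It also gives a result that largely stops depending on chance severity imbalance, in either direction. These sizes rest on the assumed gap, the severity mix, and retention unrelated to severity. Worth doing, with medium confidence in its practical size.

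**What to change.** Before unblinding:

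- Prespecify a Mantel-Haenszel risk difference with a stratified 95% CI (for example Sato variance), stratified by the severity level recorded in the IRT at randomization, with the same +20% and 0 limits. State explicitly that its continuity-correction choice is the same as for the crude interval.
- Make it primary and keep the crude interval as a sensitivity analysis. At minimum, add it to the sensitivity list in SAP 9.3.1.
- Stratify the log-rank test by the same level.
- Use severity alone. Stratifying on all eight cells costs about 1 point against severity alone (corrected power 73.6%, 75.5%, 77.8% and 81.1% at gaps 0, 20, 30 and 40).
- For restricted sensitivity sets in which a severity stratum is empty in one arm, use the crude interval.
- Name the IRT level as the stratifier whatever score is calculated later, and say which severity value SAP 9.3.4 uses. Also state how a patient is classed when the first-ranked score lies outside both bands: entry accepts APACHE II or SOFA, APACHE ranks first, and SAP 9.2.3 tabulates "APACHE II score [<10, 10 to 19, 20 to 30 and >30".

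Cost: SAP wording, a few lines of code, and carrying the IRT severity level into the analysis data.
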